## **STATISTICAL PROCEDURES**

A two-way ANOVA for repeated measures will be used to establish differences between groups and limbs. A Bonferroni post-hoc test will be used, when appropriate, to determine group differences.

Mantova, 14/06/2016, The applicant

A handwritten signature in black ink, appearing to read "[name]".

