At present, no study has shown if electrostimulation can diminish the negative effects of bed rest in the vascular functions. For this reason, the objective of this study will be to verify if electrostimulation can improve and/or reduce the negative effects of immobility on the vascular functions of the lower limbs in the bed resting elderly.

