## **METHODS**

Inclusion criteria: bed rest and walking inability for at least 6 months and no more than 2 years, age > 70 years.

Exclusion criteria: considering the type of intervention and the evaluations that will be performed, we will not include subjects presenting:

- Myocardial infarction (in the last 6 months)
- Symptomatic aortic stenosis
- Acute pulmonary embolism or pulmonary infarction
- Acute non-cardiac pathology that may be aggravated by electrostimulation (i.e. infection, renal insufficiency)
- Left coronary stenosis or equivalent
- Abnormal electrolytes blood concentration
- Atrial fibrillation with uncontrolled ventricular rate
- Cardiac pacemaker and/or defibrillator
- Use of anticoagulant drugs
- Stroke with consequent hemiparesis

The specialized geriatric medical team of the “Fondazione Mazzali di Mantova” will select 20 non-self-sufficient elders (age > 70 years), living temporarily in the nursing home of the foundation. The family members and/or legal caregivers of the residents will receive detailed information about the measurements and the purpose of the study. All the subjects will receive

an electrostimulation treatment on one of the lower limbs, while the contralateral one will only be evaluated but will not receive any treatment, acting as a control.

All the researchers and health care personnel participating in the study declared that they do not present any conflict of interest in the practice of their functions.

All the subjects will be evaluated through tests in order to determine:

- Anthropometric measures of the limbs
- Vascular functionality of the lower limbs through Echo Color Doppler with the Flow Mediated Dilation (FMD) technique with the objective to measure the residual vasodilatory capacity.
- The measurements will be repeated after an 8 months treatment, based on 30 minutes of electrostimulation, 5 days per week.
- The electrostimulation treatment will take place at the subject bed place for a duration of 30 minutes. The stimulation will be carried out with a professional stimulator (Genesy 1200 pro, Globus Italia Treviso). The electrodes will be placed in a balanced manner following the guidelines delineated by Maffiuletti et al. (12) on the lower right or left limb. As outlined in previous studies (2, 10-12), the intensity and the characteristics of the electric current used for the treatment (capillarization programme Genesy 1200 pro, Globus Italia) will be modulated based upon the subject tolerance.

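### The planned ANOVA names groups and limbs, but the design's two factors are limb and time, and no contrast is identified as the test of electrostimulation

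*Combined protocol and SAP*

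**What the plan says.** The objective, at the end of section 3, is to "verify if electrostimulation can improve and/or reduce the negative effects of immobility on the vascular functions of the lower limbs".

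METHODS describes a single cohort: the geriatric team "will select 20 non-self-sufficient elders (age > 70 years"). Every patient receives "an electrostimulation treatment on one of the lower limbs". The role of the other leg is put this way: "while the contralateral one will only be evaluated but will not receive any treatment, acting as a control". On timing: "The measurements will be repeated after an 8 months treatment".

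STATISTICAL PROCEDURES has two sentences on analysis. The first is "A two-way ANOVA for repeated measures will be used to establish differences between groups and limbs". The second is "A Bonferroni post-hoc test will be used, when appropriate, to determine group differences". Neither defines groups, names time, or says which effect answers the objective.

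**The concern.** The design is a 2 × 2 layout within each patient: limb (treated, control) by time (baseline, 8 months). The objective asks whether the treated leg fares better than the control leg over the treatment period, which is a statement about change in one leg relative to the other. The factors in the statistical section are different ones. On a natural reading, groups is either undefined or a second name for treated versus control limb. In both cases time is missing from the named comparison, and the post-hoc sentence again points to group differences.

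A two-way analysis of these data offers several candidate tests: limb, time, their interaction, and the post-hoc pairs. They estimate different quantities. With none named, the treatment test could be picked after the results are seen. One obvious candidate, the limb main effect over both visits, mixes in measurements taken before any treatment was given.

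**Working it through.** The plan gives no variance, correlation, alpha, power or derivation of the sample size, so it has no figure to reproduce. The check compares what each contrast estimates.

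**Inputs from the documents:** 20 patients, two limbs per patient, two visits.

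**Assumptions:** all 20 complete both visits; two-sided 5%; normal data; the treated-minus-control difference D has SD 1 at each visit; r is the correlation of D between visits. The true effect δ is held at 0.66 SD of D, the size that gives limb-by-time 80% power at r = 0.5.

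**What each contrast estimates.** Let D0 and D1 be the leg difference at baseline and 8 months, and s any stable difference between the legs, so that D0 has mean s and D1 has mean s + δ.

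- Limb-by-time: D1 − D0. Mean (s + δ) − s = δ; SD √(2(1 − r)).
- Limb main effect over both visits: (D0 + D1)/2. Mean δ/2 + s; SD √((1 + r)/2).

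The halving and the added s are algebra and need no assumed variance.

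**Standardised effects with s = 0.** Limb-by-time: δ/√(2(1 − r)). Limb main effect: (δ/2)/√((1 + r)/2) = δ/√(2(1 + r)). Power is from the noncentral t distribution with 19 degrees of freedom and noncentrality √20 times the standardised effect.

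| r | Limb-by-time effect | Power | Limb main effect | Power |
|---|---|---|---|---|
| 0 | 0.66/√2.0 = 0.467 | 51% | 0.66/√2.0 = 0.467 | 51% |
| 0.3 | 0.66/√1.4 = 0.558 | 66% | 0.66/√2.6 = 0.409 | 41% |
| 0.5 | 0.66/√1.0 = 0.660 | 80% | 0.66/√3.0 = 0.381 | 37% |
| 0.7 | 0.66/√0.6 = 0.852 | 95% | 0.66/√3.4 = 0.358 | 33% |

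The two tests have equal power at r = 0 and separate as r rises. At every r the main effect estimates 0.66/2 = 0.33 instead of 0.66.

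**Other analyses that the wording leaves open:**

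- Analysis of 8-month change. The limb effect is then the paired test of D1 − D0, identical to limb-by-time, with nothing lost.
- Analysis of 8-month values alone. The estimate is s + δ with SD 1. With s = 0 the standardised effect is 0.66 and power is 80% at every r. Nothing is halved.
- 8-month difference adjusted for the baseline difference. If δ is instead reset at each r so that limb-by-time has 80% power, this has 97%, 92%, 88% and 84% at r = 0, 0.3, 0.5 and 0.7.

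The last two need the treated side to be chosen at random.

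**The case against.** The best reply is that this is loose wording and the right test will be run anyway. The phrase about repeated measures may well imply time. A limb-by-time ANOVA prints the interaction as routine output, and an analysis of 8-month change gives the same test. The wording does not say which visits enter the model, so the power loss needs two further steps: including both visits, and then reading the main effect as the treatment test. Nothing in the document says that this is intended. This stands, and it limits the claim about consequences.

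A second reply is that groups may mean treated versus control and limbs may mean right versus left, since METHODS allows electrodes on either side. That would remove the duplication, but time would still be unnamed and the treatment contrast unidentified. Text before section 3 was not available to me and might define groups. The METHODS section nevertheless has every subject treated on one leg with the other as control, and a definition elsewhere would not by itself name the treatment contrast.

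A reader might also infer that the analysis as planned will produce false positives. A systematic, stable difference in the treated leg would enter the main effect, but whether one exists depends on how the side is chosen, which the text I have does not state. With a random side the tests keep close to their nominal 5% level. Limb-by-time is not a full safeguard either: it can mislead if the side is chosen on its baseline value. Those error rates are no part of this point.

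**Conclusion.** Wrong as written: the named factors do not match the design that METHODS describes, and the contrast that answers the objective is not identified. I am confident of that on the text from section 3 onwards.

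The size of the harm is conditional. It arises if both visits are modelled and the limb or group main effect is taken as the treatment test. That effect is then half the true one plus any stable leg difference, and power at r = 0.5 is 37% against 80%. The percentages rest on the assumed effect, correlation, alpha and complete follow-up.

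It would be too strong to conclude that repeated-measures ANOVA is the wrong method, or that limb-by-time is the only valid test. ANOVA with the right factors contains a suitable test, and the data to be collected support it. The point should be fixed because, with 20 patients, the choice among unnamed contrasts can change the conclusion.

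**What to change.** Replace the first sentence of STATISTICAL PROCEDURES with:

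> A two-way repeated-measures ANOVA with limb (treated, control) and time (baseline, 8 months) as within-patient factors will be used for each outcome; the limb-by-time interaction, equal to a paired test of the treated-minus-control difference in 8-month change, is the test of treatment and is reported with its 95% confidence interval.

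Replace the second with:

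> Bonferroni-adjusted simple-effect comparisons (change over time within each limb; treated versus control limb at each visit) are supportive and do not replace the interaction test.

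If the treated side is chosen at random, a baseline-adjusted paired comparison at 8 months may be named instead; it is at least as powerful under the assumed values. The plan should commit to one of the two.

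The cost is the rewording of two sentences, with no added patients, visits or measurements. The primary outcome, alpha, incomplete patients and the choice of side are separate matters that this change does not settle.

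### A cheap improvement, not an error: allocate the stimulated leg by concealed randomisation and, once that is in place, adjust the 8-month leg difference for the baseline leg difference

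*Combined protocol and SAP*

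**What the plan says.** Methods: the team "will select 20 non-self-sufficient elders". Each receives "an electrostimulation treatment on one of the lower limbs"; the opposite leg is measured but left unstimulated, as the comparator. The only wording on which leg is stimulated is "on the lower right or left limb". The reference to balance in that sentence concerns electrode placement, not allocation of the leg. No random or other selection rule appears.

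The outcomes are "Anthropometric measures of the limbs" and lower-limb FMD, and neither is labelled primary. "The measurements will be repeated after an 8 months treatment", so both legs have a baseline value.

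Statistical Procedures: "A two-way ANOVA for repeated measures will be used to establish differences between groups and limbs", followed by Bonferroni post-hoc tests. Time, the treatment contrast and a baseline covariate are not named. The visible text gives no SD, correlation, effect size, alpha, power or dropout rate.

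**The concern.** A within-patient design is a sensible choice at this sample size, but the comparison is only as good as the way the treated leg is picked. Two kinds of non-random choice cause different problems:

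- **The leg is chosen because its baseline FMD is low.** Part of a low reading is chance and recovers at the next visit. The treated leg then appears to gain on its control without any effect of stimulation, which biases a change analysis.
- **The leg is chosen in a way that tracks a stable difference between legs.** A change analysis cancels such a difference. An analysis that adjusts for baseline cancels only part of it, and is biased.

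No choice of analysis is therefore safe against both, whereas random allocation of the leg removes both. Once the leg is random, what remains is precision: a change contrast fixes the weight on baseline at 1, whereas a regression estimates the weight from data already being collected.

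**Working it through.** **Inputs.** From the Methods: 20 patients, one treated and one control leg each, two visits. Assumed, because the documents are silent: two-sided alpha 0.05; normal data; r from 0.3 to 0.8, where r is the correlation between baseline and 8-month treated-minus-control differences; equal SDs at the two visits unless stated; an effect giving the change analysis 80% power at n=20. There is no power statement in the plan to reproduce.

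**Step 1: what the planned ANOVA tests.** There is one group of patients, so the two factors are read here as limb and time (an inference). The limb-by-time F then equals the squared paired t on the change in leg difference; on a simulated data set both were 0.4127. At n=20 this test has 80% power for an effect of 0.660 SD of that change.

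**Step 2: non-random leg, no true effect.** Take the SD of the leg difference as 1. If the lower-baseline leg is always treated, the expected spurious change is (1−r)×√(2/π) = (1−r)×0.798. If it is treated in 75% of patients, multiply by 0.75−0.25 = 0.5. False-positive rates are simulated:

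| r | Spurious change, always | Change test, always | Spurious change, 75% | Change test, 75% |
|---|---|---|---|---|
| 0.3 | 0.56 SD | 62% | 0.28 SD | 18% |
| 0.5 | 0.40 SD | 45% | 0.20 SD | 14% |
| 0.7 | 0.24 SD | 28% | 0.12 SD | 10% |
| 0.8 | 0.16 SD | 20% | 0.08 SD | 8% |

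The adjusted test stays at 5% throughout, but only because selection here depends solely on the measured baseline. With a stable leg difference of 0.25 or 0.5 SD at r=0.5, the adjusted test rises to 9% or 19% and the change test stays at 5%.

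**Step 3: random leg, type I error.** The change, plain 8-month and adjusted analyses all gave 4.9–5.2%. The choice among them is about precision only.

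**Step 4: random leg, precision.** With k the 8-month SD divided by the baseline SD, variances are proportional to:

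- change: 1+k²−2rk
- plain 8-month difference: k²
- adjusted: k²(1−r²)(n−2)/(n−3)

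At k=1, adjusted/change = ((1+r)/2)×(n−2)/(n−3). For n=20 the last factor is 18/17, about 6% extra variance for estimating the slope. Simulated power, with 100,000 trials per setting:

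| r | Adjusted/change variance | Change | Plain 8-month | Adjusted | Gain over better simple analysis |
|---|---|---|---|---|---|
| 0.3 | 0.65×18/17 = 0.688 | 80% | 91% | 92% | about 1 point |
| 0.5 | 0.75×18/17 = 0.794 | 80% | 80% | 88% | about 8 points |
| 0.7 | 0.85×18/17 = 0.900 | 80% | 58% | 84% | about 4 points |
| 0.8 | 0.90×18/17 = 0.953 | 80% | 42% | 82% | about 2 points |

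The effect is rescaled at each r to hold the change analysis at 80%, so the rows do not describe one common treatment effect.

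**Step 5: where adjustment does not pay.** Break-even in variance against the change score is r = 2(n−3)/(n−2)−1. This is 2(17/18)−1 = 0.89 at n=20 and 2(11/12)−1 = 0.83 with 14 completers. Against the plain 8-month difference at n=20 it is √(1−17/18) = 0.24.

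If the SD rises by 8 months, adjusted power at n=20 (change = 80%) is 87, 82, 78 and 78% for k=1.25 and 83, 79, 78 and 80% for k=1.5, at r=0.3, 0.5, 0.7 and 0.8. The worst loss is about 2.5 points.

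With 14 completers and the same effect, the change analysis has 63%. The adjusted analysis has 71% at r=0.5 with equal SDs; 60% and 59% at k=1.25 with r=0.7 and 0.8; and 60% and 59% at k=1.5 with r=0.5 and 0.67. The loss reaches about 4 points.

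**The case against.** **Nothing shows that the leg will be chosen badly.** This stands. A reader might infer from the error rates that the trial is biased, but the documents do not say that staff favour either leg. The rates show what an unstated rule could allow. A randomisation statement in the unavailable opening pages also cannot be excluded, although the Methods, where one would expect it, contain none.

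**The planned ANOVA is valid.** This also stands once the leg is random. A reader might infer that the analysis is wrong or the trial underpowered, and the documents support neither. The limb-by-time comparator is inferred, and its 80% power is an assumption made here.

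**Against a fair comparator the gain is modest.** With a random leg, limb-by-time is not the only valid contrast, because the plain 8-month difference is valid too. Comparing adjustment with the change score alone would flatter it at low r. The gain is therefore quoted against the better of the two. In favour of adjustment, r is unknown beforehand, so the better simple analysis cannot be picked in advance.

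**Adjustment can lose power.** It can, and more so with fewer completers. Eight months in bed-resting people over 70 makes fewer than 20 completers plausible, though no dropout rate is given.

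A further tempting inference is that adjustment can stand in for randomisation. The stable-difference case (9% or 19%) shows that it cannot.

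**Conclusion.** The point holds as a low-cost improvement. Its main part is the missing rule for choosing the leg, since a concealed random choice protects every analysis considered here. The size of any bias without it is unknown; the illustrative error rates depend wholly on the assumed selection rule and on r. Randomising the leg does not address unblinded ultrasound reading, carry-over of stimulation to the control leg, or dropout.

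Baseline adjustment is secondary and conditional on randomisation. It is worth most at middling r, little at r=0.3 or 0.8, and nothing beyond break-even when the SDs are equal. All power figures rest on the assumed inputs listed in the working.

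**What to change.** 1. **Add to Methods:** *The leg to be stimulated is allocated at random for each patient, from a computer-generated list concealed until the baseline FMD measurement is complete; patients are analysed by the allocated leg.*

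2. **With item 1 in place, add to Statistical Procedures:** *The 8-month treated-minus-control FMD difference is regressed on the baseline treated-minus-control FMD difference, one row per patient. The treatment effect is the intercept at a baseline difference of zero, with its 95% confidence interval; the covariate is not centred at its sample mean. The limb-by-time interaction is the supporting ANOVA contrast.* Whether FMD is the primary outcome is a separate decision for the sponsor.

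3. **If the leg is not randomised:** report how it was chosen and show both the change and the adjusted analysis, stating that neither is generally unbiased.

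**Cost:** an allocation list, someone to hold it, and a few sentences of text. The regression uses one error degree of freedom (19 to 18) and carries the possible power loss given above. No extra patients or measurements are needed.
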